7.7. Adverse events

All adverse event data (serious and non-serious) for the duration of the study will be reported and coded to MedDRA classification system.

Adverse event counts by number of events and people will be summarised by group. Also, adverse event counts by categories collected in the adverse event form (type, relationship to study treatment and seriousness) will be summarised and separate table will also be given for the incidence rate ratios comparing the intervention arms. Line listings will also be produced in order to examine all serious adverse events and multiple adverse events for a participant on the same date.

Additional adverse event analysis related to the CONSORT harms extension will be conducted where possible.

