1. STUDY OBJECTIVES

The primary objective of this trial is to evaluate the effectiveness, safety, and acceptability of combining cytisine with nicotine e-cigarettes plus text-based behavioural support (TBS), compared to cytisine plus TBS or nicotine e-cigarettes plus TBS, on six-month smoking abstinence.

We hypothesise that cytisine plus nicotine e-cigarettes and TBS is more effective at helping smokers quit than cytisine plus TBS. Furthermore, cytisine plus nicotine e-cigarettes and TBS is more effective at helping smokers quit than nicotine e-cigarettes plus TBS.

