2. STUDY DESIGN

Please refer to the study protocol for a full description of the trial design. This is a single-blind, pragmatic three-arm, parallel group, randomised trial. Participants will be recruited nationwide, using multi-media advertising with targeted promotion to reach Māori, Pacific and low socio-economic groups given their disproportionately higher smoking prevalence.

Potential participants interested in the trial will register on a trial website. Participants will be asked for on-line consent to complete an online screening questionnaire to determine their eligibility for the trial and verify their phone number. Eligible and interested participants will then provide online consent to enter the trial.

A copy of the consent form and participant information sheet will be automatically emailed by the online system to the participant for their records. Participants will also be asked to provide online consent to inform their general practitioner that they are participating in the trial. Via the online platform the baseline data will be collected, and then participants will immediately be randomised to either 12 weeks of: 1) cytisine plus nicotine e-cigarette, 2) cytisine; or 3) nicotine e-cigarette.

All 12-weeks of trial products will be couriered to participants immediately after randomisation. The courier company will notify the study centre immediately after the courier pack has been delivered, which will trigger the scheduling of the 'quit date' follow-up call and the start of the text-based behavioural support programme. Participants will be asked to begin their treatment the day after they receive their courier pack and to reduce their smoking *ad libitum* over the first four days of treatment so that they are not smoking at all by the fifth day ('quit date').

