Participants will be called on their quit date to verify they are quitting on that day (and to collect outcome data). If a participant states that they are not quitting on the scheduled 'quit date', they will be given one chance to reset their quit date within the next seven days, with this date becoming their new 'quit date' (which will trigger the scheduling of all subsequent follow-up calls). For participants who are unable to be contacted at quit date, their 'quit date' will be set in the system as six days after they received their courier pack (which will trigger the scheduling of all subsequent follow-up calls). Participants will be advised to continue with their allocated treatment irrespective of any lapses back to smoking.

Outcome assessments will be undertaken at one, three, and six months after the Quit date, and at 12 months in a subsample. At the six-month follow-up, in-person carbon monoxide tests will be performed for participants who live in the Auckland region to verify self-reported continuous smoking abstinence.

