2.2. Study intervention

Participants allocated cytisine will be instructed to follow the manufacturer's 25-day dosing regimen:

- days 1-3: one tablet (1.5mg) every two hours through the waking day (six tablets/day)
- days 4-12: one tablet every 2.5 hours (five tablets/day)
- days 13-16: one tablet every three hours (four tablets/day)
- days 17-20: one tablet every 4-5 hours (three tablets/day)
- days 21-25: one tablet every six hours (two tablets/day)

However, a maintenance dose of cytisine will be added for day 26 to week 12 (one tablet every six hours: two tablets/day).

Participants allocated a nicotine e-cigarette will be instructed to follow the manufacturer's instructions for use, with ad libitum use over 12 weeks. The e-cigarette device used in the trial will be the 'UpOX', a closed pod system with a 3% nicotine salt (30mg/mL). A tobacco flavour e-liquid will be provided as this is the usual flavour chosen by smokers when they are transitioning away from tobacco. Participants will be advised that they should try and use only the product provided,

but if they are finding the nicotine strength is not sufficiently addressing their cravings (or the flavour is distasteful) they are free to try alternative nicotine strengths or flavours, but that this will be at their own cost). Participants will be asked at follow-up about any switching of products. The content of the nicotine e-liquid supplied will be independently assessed (by LabTech Scientific and Technical Services, Auckland) to verify nicotine content is as labelled. Batch-to-batch variability in nicotine content in the e-liquids will also be assessed.

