- **Adverse events and serious adverse events**: self-reported adverse events are collected at each follow-up call, with adverse events coded using MedDRA. In addition, participants can at any time report an adverse event via a web-based adverse event diary.

- **Change from baseline in weight and body mass index** (three and six months)
- **Change from baseline in general health** (three, six and 12 months): shortness of breath, cough, asthma, chronic pain, COPD, and mental health. Measured for participants who answered Yes to the general health question at baseline, and is measured using a five-point scale (much worse, a bit worse, about the same, a bit better, much better).
- **Concomitant medication:** other medications taken during the course of the study
- **Cost outcomes:** cost-per- quitter, cost-per-person reducing their daily cigarette consumption, and the incremental cost-effectiveness ratio
- **Text-based behavioral support STOMP program received:** total number received up until end of the six month follow-up or they opt out of receiving the messages.

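### SAP Section 7.7 gives its adverse-event rate ratios no treatment-period window or time at risk, so harms confined to product use would be diluted by later follow-up

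*SAP*

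**What the plan says.** Section 1 makes safety part of the primary objective: the trial is to "evaluate the effectiveness, safety, and acceptability of combining cytisine with nicotine e-cigarettes".

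On exposure, Section 2 says "All 12-weeks of trial products will be couriered to participants immediately after randomisation". Section 2.2 adds to the 25-day cytisine regimen that "a maintenance dose of cytisine will be added for day 26 to week 12". Planned cytisine exposure therefore ends at week 12.

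On follow-up, Section 2 says "Outcome assessments will be undertaken at one, three, and six months after the Quit date, and at 12 months in a subsample". Under Section 4.2, "self-reported adverse events are collected at each follow-up call", and "participants can at any time report an adverse event via a web-based adverse event diary".

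On analysis, Section 7.7 opens with "All adverse event data (serious and non-serious) for the duration of the study will be reported and coded to MedDRA classification system". It then plans counts by group, counts by type, relationship to treatment and seriousness, and says that a "separate table will also be given for the incidence rate ratios comparing the intervention arms". It does not state which events enter the rate ratios, what person-time is the denominator, or whether events before and after week 12 are separated.

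**The concern.** An incidence rate ratio has no fixed meaning until its time at risk is stated. The only window named in Section 7.7 is the whole study, so an analyst following the text would most naturally divide all events by all follow-up time.

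More than half of the six-month follow-up falls after the product supply ends. In the comparison of the combination with the e-cigarette alone, the added exposure is cytisine, which is planned to stop at week 12. If its harms occur while it is taken, events after week 12 are background in both arms and move the ratio towards 1. This is the only between-arm adverse-event estimate that the SAP names, and it bears on a stated part of the primary objective. A moderate excess during treatment could then appear small, or go unnoticed among background events.

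**Working it through.** The SAP gives no adverse-event rate, rate ratio or safety power, so there is no planned figure to reproduce. The calculation shows how far a treatment-period ratio shrinks under stated assumptions.

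**Inputs from the SAP**
- Treatment period: 12 weeks (Sections 2 and 2.2).
- Follow-up for all: six months after the quit date, taken as 26 weeks, as Section 2.2 does for the text programme.
- Planned sizes: 300 in the combination arm and 200 in the e-cigarette arm (Section 2.4).
- Planned loss: 28% at six months (Section 2.4).
- Tests: two-sided, 5% level (Section 7).

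**Assumptions, not in the SAP**
- R is the true on-treatment rate ratio, and the ratio is 1 after week 12.
- b is the off-treatment event rate relative to the on-treatment control rate.

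**Off-treatment share of follow-up:** (26 − 12)/26 = 14/26 = 54%.

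**Pooled ratio over 26 weeks, no loss:** (12R + 14b)/(12 + 14b).

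| b | R = 1.5 | R = 2.0 |
|---|---|---|
| 1 | (18 + 14)/26 = 1.23 | (24 + 14)/26 = 1.46 |
| 0.5 | (18 + 7)/19 = 1.32 | (24 + 7)/19 = 1.63 |
| 0.25 | (18 + 3.5)/15.5 = 1.39 | (24 + 3.5)/15.5 = 1.77 |

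Counting in days from treatment start changes little. Treatment begins four days before the quit date, so follow-up is 4 + 182 = 186 days, of which 84 (45%) are on treatment. For R = 2.0 and b = 1 the pooled ratio is 1 + 84/186 = 1.45.

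**Effect of loss.** If 28% are lost for the whole off-treatment period, the off-treatment time is 14 × 0.72 = 10.08 weeks. With b = 1:
- R = 2.0 becomes (24 + 10.08)/22.08 = 1.54.
- R = 1.5 becomes (18 + 10.08)/22.08 = 1.27.

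**Effect on detection (illustrative).** Take R = 1.5, b = 1, no loss, Poisson counts and an assumed 0.3 events per control participant per 12 weeks. The standard error of the log ratio is √(1/E1 + 1/E0), where E1 and E0 are the expected events in the combination and e-cigarette arms.
- Treatment period: E1 = 300 × 0.3 × 1.5 = 135 and E0 = 200 × 0.3 = 60. SE = 0.155, z = 0.405/0.155 = 2.61, power 74%.
- 26 weeks: E1 = 90 × (1.5 + 14/12) = 240 and E0 = 60 × (26/12) = 130. SE = 0.109, z = 0.208/0.109 = 1.91, power 48%.

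With R = 2.0 and 0.1 events per control participant per 12 weeks, the same method gives 77% and 54%. The added follow-up brings more events, yet the chance of seeing the treatment-period excess falls.

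**The case against.** **The SAP already separates time to some extent.** Adverse events are listed among the secondary outcomes in Section 4.2, and Section 7.6 promises descriptive summaries of all secondary outcomes by visit and group. The three-month call falls about 4 + 91 − 84 = 11 days after the supply ends, so reports up to that call are mostly from the treatment period. Section 7.7 also tabulates events by relationship to treatment and leaves room for further harms analyses under CONSORT. This stands, and it means that a treatment-period excess would not be wholly hidden. But these are descriptive counts, judged categories or unspecified analyses. None is a treatment-period rate ratio with matching person-time.

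**The pooling is inferred.** A reader might take it as stated that the rate ratios cover all follow-up. The opening sentence of Section 7.7 governs which data are reported and coded; the rate-ratio sentence names no window. The table shells are in a separate file (Section 7, Appendix I) that is not at hand. This stands as a limit on the claim, though the silence is itself what needs correcting.

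**The constant-background case is near the worst.** Scheduled calls are front-loaded (quit date, one and three months, then six), so reporting may fall after week 12, and some participants will be lost. The lower values of b and the 28% loss above show less dilution, but some remains in every case.

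**Two broader readings go too far.** One is that every harm is diluted. Delayed effects, or effects of stopping, are not diluted in this way. Section 4.2 also measures continued use after three months, so exposure may not end at week 12; this matters most for the combination against cytisine, where the added product is the e-cigarette. The other is to run the sum to 12 months, which turns 2.0 into (24 + 40)/52 = 1.23. That would need everyone followed for 12 months, and Section 2 limits this to a subsample of unstated size.

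**A whole-study comparison is legitimate.** It fits the intention-to-treat rule in Section 6.1 and captures late events. This stands: the case is for adding a treatment-period estimate, not for removing the whole-study one. Nor does the SAP plan any non-inferiority or equivalence claim on safety, so one cannot infer that the trial would declare the combination as safe as the single products.

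**Conclusion.** The point holds as a gap in specification with a predictable direction of bias for one class of harm. Section 7.7 promises between-arm rate ratios without a time at risk or a treatment-period window, in a trial with 12 weeks of product and at least six months of follow-up.

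On the likelier whole-study reading, and with no off-treatment effect and no loss, an on-treatment ratio of 2.0 would appear as about 1.46 to 1.77, and 1.5 as about 1.23 to 1.39. The range depends on whether off-treatment reporting stays constant or falls to a quarter of the on-treatment control rate. The event rates, R and b are all assumptions, since the SAP gives none. The figures apply best to cytisine harms in the combination against the e-cigarette alone, and overstate the dilution where use continues after week 12.

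The documents do not support saying that the whole-study analysis is wrong or that harms would go unreported. This is an inexpensive improvement to a safety analysis that serves the primary objective.

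**What to change.** In Section 7.7:
- State the time at risk for the whole-study rate ratio, including how the 12-month subsample, withdrawal and loss to follow-up enter the person-time.
- Pre-specify, alongside it, an incidence rate ratio and the proportion with at least one event for events with onset from treatment start to the end of the 12-week treatment period, plus a short lag fixed in advance. Use that period's person-time as the denominator of the rate ratio.
- Keep the whole-study table, so that late events remain visible.

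The data appear to be available: there is a three-month call, a diary open at any time, and Section 7.7 plans listings of multiple events by date, which implies that dates are recorded.

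The cost is a change of SAP wording and one extra set of tables. The treatment-period table will hold fewer events, and some onset dates will rest on recall between calls. Fixing the window and lag before the data are seen also prevents a choice made on the results.

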8. PEER REVIEW

The statistical analysis and report for the primary outcome will be peer reviewed by an independent member of the NIHI Biostatistics team (not involved in the study).
